| RV | Rotavirus |
| SAE | Serious adverse event |
| SAP | Statistical Analysis Plan |
| SBIR | GSK Biological's Internet Randomization System |
| SD | Standard Deviation |
| TFL | Tables Figures and Listings |
| TOC | Table of Content |
| TVC | Total Vaccinated Cohort |
| UL | Upper Limit of the confidence interval |
| U/ml | Unit per milliliter |

1. DOCUMENT HISTORY

| Date | Description | Protocol Version |
|-------------|--------------------------|---------------------|
| 12-SEP-2016 | Version 1: first version | Final – 03-JUN-2016 |

2. STUDY DESIGN

N = Number of subjects planned to be enrolled; n = Number of subjects in each group; BS = Blood Sampling. Visit 3 and Visit 5 are applicable only for subjects in the Staggered group. Visit 4 is applicable only for subjects in the Co-administration group.

- Experimental design: Phase IV, open-label, randomised, controlled, multi-centric, single-country study with two parallel groups.
- Primary Completion Date: Visit 7 (Month 5)
- End of Study: Last testing results released of samples collected at Visit 7
- Study groups: The study groups and epoch foreseen in the study are provided in Table 1.

Table 1 **Study groups and epochs foreseen in the study**

| Study Groups | Number of subjects | Age (Min/ - Max) | Epoch |
|-------------------------|--------------------|--------------------|-----------|
| | | | Epoch 001 |
| Co-administration group | 146 | 6 weeks - 12 weeks | x |
| Staggered group | 146 | 6 weeks - 12 weeks | x |

- The study groups and treatment foreseen in the study are provided in Table 2.

Table 2 Study groups and treatment foreseen in the study

| Treatment name | Vaccine name | Study Groups | |
|----------------|--------------|-------------------------|-----------------|
| | | Co-administration group | Staggered group |
| Rotarix | HRV | x | x |
| Squarekids | Squarekids | x | x |

- Control: active control (Staggered group).
- Vaccination schedules: The vaccination schedules are as follows:
 - Subjects in the Co-administration group will be administered the DPT-IPV vaccine according to a 3, 4, 6 month schedule and the liquid HRV vaccine according to a 2, 3 month schedule.
 - Subjects in the Staggered group will be administered the DPT-IPV vaccine according to a 3, 4.5, 6 month schedule and the liquid HRV vaccine according to a 2, 3.5 month schedule.
- Treatment allocation: Randomised 1:1 using GSK Biologicals' central randomisation system on Internet (SBIR). The randomisation algorithm will use a minimisation procedure accounting for centre and stratified for a HRV immunogenicity sub-cohort.
- Blinding: Open-label.
- Sampling schedule: Details of the samples to be collected are as follows:
 - A blood sample of approximately 2 mL will be collected from a sub-cohort of subjects, 1 month after the administration of the second dose of the liquid HRV vaccine.
 - A blood sample of approximately 5 mL will be collected at Visit 7, 1 month after administration of the last dose of DPT-IPV vaccine from all the subjects.
- Details of the HRV Immunogenicity sub-cohort are provided in Table 3. The sub-cohort will consist of 146 subjects (the first 73 subjects enrolled into the study from each study group).

Table 3 Sub-cohorts

| Sub-cohort name | Description | Estimated number of subjects |
|-------------------------------|--|--|
| HRV Immunogenicity sub-cohort | The serum anti-RV IgA antibody concentration and seropositivity 1 month after the second dose of the liquid HRV vaccine will be assessed in this sub-cohort of subjects. | 146 subjects (approximately half the number of subjects (73) from each study group)* |

* The first 73 subjects enrolled into each study group will be allocated to the sub-cohort.

- Recording of solicited local symptoms within 8 days follow-up period (Day 0 - Day 7) after the first dose of DPT-IPV vaccine.

- Recording of solicited general symptoms within 8 days follow-up period (Day 0 - Day 7) following administration of each dose of HRV vaccine and after the first dose of DPT-IPV vaccine.
- Recording of unsolicited symptoms within 31 days (Day 0- Day 30) following administration of each dose of HRV vaccine and after the first dose of DPT-IPV vaccine.
- Recording of causally related AEs from the first study vaccine up to Visit 7.
- Recording of SAEs from first study vaccine up to Visit 7.
- Recording of AEs/SAEs leading to withdrawal from the study from the first study vaccine.
- Recording of SAEs that are related to study participation (i.e. protocol-mandated procedures, invasive tests, a change from existing therapy) or are related to a concurrent GSK medication/vaccine from the time the subject consents to participate in the study until Visit 7.
- Type of study: self-contained.
- Data collection: Electronic Case Report Form (eCRF).

3. OBJECTIVES

3.1. Primary objective

- To demonstrate that the immunogenicity to the antigens contained in DPT-IPV vaccine is not impaired by the co-administration with GSK Biologicals' liquid HRV vaccine.

Criteria for non-inferiority (1 month after the third dose of DPT-IPV vaccine at Visit 7):

- Lower limits of the standardised asymptotic 95% confidence intervals (CIs) on the differences (Co-administered group minus Staggered group) in the percentages of subjects with seroprotective concentrations ≥ 0.1 IU/mL for anti-diphtheria (anti-D) antibodies and concentrations ≥ 0.1 IU/mL for anti-tetanus (anti-T) antibodies are $\geq -10\%$ (clinical limit for non-inferiority),
- Lower limits of the 95% CIs on the differences (Co-administered group minus Staggered group) in the percentages of subjects with concentrations ≥ 10 IU/mL for antibodies against the pertussis toxoid (PT) and filamentous hemagglutinin (FHA) antigens (anti-PT and anti-FHA) are $\geq -10\%$ (clinical limit for non-inferiority),
- Lower limits of the standardised asymptotic 95% CIs on the differences (Co-administered group minus Staggered group) in the percentages of subjects with seroprotective titres (≥ 8 ED₅₀) for each of anti-poliovirus serotypes 1, 2 and 3 antibodies are $\geq -10\%$ (clinical limit for non-inferiority).

3.2. Secondary objectives

- To assess the immunogenicity of the liquid HRV vaccine in terms of serum anti-RV IgA antibody seropositivity and Geometric Mean Concentrations (GMCs) in a sub-cohort of subjects, 1 month after the second dose of the liquid HRV vaccine.
- To assess the immunogenicity to all the antigens contained in the DPT-IPV vaccine in terms of GMCs/ geometric mean antibody titres (GMTs), 1 month after the third dose of the DPT-IPV vaccine.
- To assess reactogenicity and safety after each dose of liquid HRV vaccine and first dose of DPT-IPV vaccine in terms of solicited symptoms during the 8-day follow-up period and unsolicited symptoms during the 31-day follow-up period.
- To assess safety in terms of serious adverse events (SAEs) from the first dose of study vaccine up to study end.

4. ENDPOINTS

4.1. Primary endpoint

- Immunogenicity with respect to components of the DPT-IPV vaccine 1 month after administration of the third dose of the vaccine (Visit 7):
 - anti-diphtheria antibody concentrations ≥ 0.1 IU/mL,
 - anti-tetanus antibody concentrations ≥ 0.1 IU/mL,
 - anti-PT and anti-FHA antibody concentrations ≥ 10 IU/mL,
 - anti-poliovirus serotypes 1, 2 and 3 antibody titre ≥ 8 ED₅₀.

4.2. Secondary endpoints

- Serum anti-RV IgA antibody concentration and seropositivity in a sub-cohort of subjects, 1 month after the second dose of the liquid HRV vaccine.
- Serum GMCs/GMTs for anti-diphtheria, anti-tetanus, anti-poliovirus serotypes 1, 2 and 3, anti-PT and anti-FHA antibodies, 1 month after the third dose of the DPT-IPV vaccine.
- Occurrence of solicited general symptoms during the 8-day (Days 0-7) follow-up period after each dose of liquid HRV vaccine.
- Occurrence of solicited local and general symptoms during the 8-day (Days 0-7) follow-up period after the first dose of DPT-IPV vaccine.
- Occurrence of unsolicited AEs during the 31-day (Days 0-30) follow-up period after each dose of the liquid HRV vaccine and the first dose of DPT-IPV vaccine, according to the Medical Dictionary for Regulatory Activities (MedDRA) classification.
- Occurrence of SAEs from the first dose of the study vaccine up to study end (Visit 7).

5. ANALYSIS SETS

5.1. Definition

Two cohorts are defined for the purpose of the analysis:

- Total vaccinated cohort.
- ATP cohort for analysis of immunogenicity.

5.1.1. Total vaccinated cohort

The TVC will include all subjects with at least one dose of the study vaccines administration documented:

- A safety and reactogenicity analysis based on the TVC will include all subjects with at least one vaccine administration documented.
- An immunogenicity analysis based on the TVC will include all subjects from this cohort for whom immunogenicity data were available.

The TVC analysis will be performed per treatment actually administered.

5.1.2. According-to-protocol cohort for analysis of immunogenicity

The ATP cohort for immunogenicity will include all eligible subjects:

- who comply with vaccination schedule of DPT-IPV and HRV vaccines,
- for whom the DPT-IPV and HRV vaccines were administered according to protocol
- who have not received vaccine/medication forbidden by the protocol (up to Visit 7),
- whose underlying medical condition was not forbidden by the protocol (up to Visit 7),
- who complied with the blood sampling schedule at visit 7,
- who had no concomitant infection related to any component of the DPT-IPV vaccine which may have influenced the immune response up to blood sample at visit 7,
- who had no concomitant infection unrelated to any component of the DPT-IPV vaccine which may have influenced the immune response up to blood sample at visit 7. Note that RV GE will not be considered as concomitant infection unrelated to any component of the DPT-IPV vaccine.
- for whom immunogenicity data are available for at least one antigen of the DPT-IPV vaccine at visit 7 sampling time point.

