5.2.2. Elimination from ATP cohort for analysis of immunogenicity

A subject will be excluded from the ATP cohort for analysis of immunogenicity under the following conditions:

| Code Eli Type =MA | Condition under which the code is used |
|----------------------|---|
| 900 | Invalid informed consent or fraud data |
| 1030 | Study vaccine dose not administered at all but subject number allocated |
| 1040 | Administration of concomitant vaccine(s) forbidden in the protocol up to blood sample at visit 7 |
| 1050 | Randomisation failure (subject not randomized in the correct group) |
| 1070 | Study vaccine dose not administered according to protocol: - Site or route of study vaccine administration wrong or unknown - Administration not according to protocol for reason specified by the investigator other than site and route - Wrong replacement or study vaccine administered (not compatible with the vaccine regimen associated to the treatment number) - Only part of the multiple planned administrations at one visit has been administered |
| 1080 | Vaccine has been administered (effective treatment number) despite a temperature deviation qualified by Status QA GMP NON Use |
| 1090 | Vaccine has been administered (effective treatment number) out of the expiration date at the time of administration |
| 2010 | Protocol violation linked to the inclusion/exclusion criteria |
| 2040 | Administration of any medication forbidden by the protocol up to blood sample at visit 7 |
| 2050 | Underlying medical condition forbidden by the protocol up to blood sample at visit 7 |
| 2060 | Concomitant infection related to any component of the DPT-IPV vaccine which may influence the immune response up to blood sample at visit 7 |
| 2070 | Concomitant infection not related to any component of the DPT-IPV vaccine other than RV GE which may influence the immune response up to blood sample at visit 7. Note that RV GE will not be considered as concomitant infection unrelated to any component of the DPT-IPV vaccine. |
| 2080 | Non compliance with vaccination schedule for HRV and/or DPT-IPV vaccination – see Table 4 |
| 2090 | Non compliance with blood sample schedule at Visit 7 – see Table 4 |

| Code Eli Type =MA | Condition under which the code is used |
|----------------------|---|
| 2100 | Essential serological data missing: serological data missing for all antigens in the DPT-IPV vaccine at Visit 7 |

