5.2.4. Visit-specific censored Data

Not applicable.

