6.3. Immunogenicity

6.3.1. Analysis of immunogenicity planned in the protocol

The ATP cohort for immunogenicity will be used for the primary analysis of immunogenicity. An analysis of immunogenicity based on the TVC will be performed

only if more than 5% of the vaccinated subjects with immunogenicity results available were excluded from the ATP cohort for immunogenicity. In such a case, the TVC analyses will evaluate whether exclusion from the ATP cohort has biased the results.

Within group assessment

For each treatment group and each antigen:

- Percentage of subjects with antibody concentrations/ titres greater than or equal to the pre-specified cut-off will be calculated with exact 95% CI (Refer Table 9 of the protocol). Anti-PT and anti-FHA antibody concentrations ≥ 10 IU/mL will also be calculated with exact 95% CI.
- GMC/GMTs, as applicable with 95% CIs will be computed.
- The distribution of antibody concentrations/ titres, as applicable, will be presented using reverse cumulative curves (RCCs).

Between group assessment

For each antigen in the DPT-IPV vaccine:

- The two-sided asymptotic standardised 95% CIs for the difference between groups (Co-administration group minus Staggered group) in terms of percentage of subjects with antibody concentrations/ titres greater than or equal to the pre-specified cut-off will be computed. Anti-PT and anti-FHA antibody concentrations ≥ 10 IU/mL will also be calculated with exact 95% CI.

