| | | Age | PRE-Dose:1 | Dose:1-Dose:2 | | Dose:2-PII(M2) | |
|---------|----------|--------------------|------------------|--------------------|--------------------|--------------------|--------------------|
| Group | Protocol | Protocol | Protocol | Adapted | Protocol | Adapted | |
| | | from 6 to 14 weeks | from 0 to 0 days | from 30 to 48 days | from 21 to 48 days | from 30 to 48 days | from 21 to 48 days |
| HRV | N | 508 | 37 | 499 | 499 | 35 | 35 |
| | n | 0 | 0 | 0 | 0 | 0 | 0 |
| | % | 0.0 | 0.0 | 0.0 | 0.0 | 0.0 | 0.0 |
| | range | 6 to 14 | 0 to 0 | 30 to 47 | 30 to 47 | 30 to 45 | 30 to 45 |
| Placebo | N | 257 | 20 | 250 | 250 | 20 | 20 |
| | n | 1 | 0 | 0 | 0 | 0 | 0 |
| | % | 0.4 | 0.0 | 0.0 | 0.0 | 0.0 | 0.0 |
| | range | 5 to 14 | 0 to 0 | 30 to 47 | 30 to 47 | 30 to 42 | 30 to 42 |

Adapted = interval used for defining the ATP cohorts for immunogenicity

N = total number of subjects with available results

n (%) = number / percentage of subjects with results outside of the interval

range = minimum-maximum for age and intervals

PRE = pre-vaccination

PII(M2) = One month after the second dose (Visit 3)

Template 9 Study population (Total vaccinated cohort)

| Number of subjects | [each group] | Total |
|--|--------------|-------|
| Planned, N | | |
| Randomised, N (<Total Vaccinated Cohort>) | | |
| Completed, n (%) | | |
| Demographics | | |
| N (<Total Vaccinated Cohort>) | | |
| Females:Males | | |
| Mean Age, <years> (SD) | | |
| Median Age, <years> (minimum, maximum) | | |
| <Most frequent category of race>, n (%) | | |
| <Second most frequent category of race>, n (%) | | |
| <Third most frequent category of race>, n (%) | | |

[each group]:

Short group label= long group label

Template 10 Anti-rotavirus IgA antibody GMC and seropositivity rates - ATP cohort for immunogenicity

| | | | $\geq 20 \text{ U/mL}$ | | | | GMC | | | |
|---------|---------|----|------------------------|------|--------|------|-------|-------|--------|--|
| | | | | | 95% CI | | | | 95% CI | |
| Group | Timing | N | n | % | LL | UL | value | LL | UL | |
| HRV | PRE | 34 | 0 | 0.0 | 0.0 | 10.3 | <20 | - | - | |
| | PII(M2) | 34 | 29 | 85.3 | 68.9 | 95.0 | 217.0 | 109.9 | 428.6 | |
| Placebo | PRE | 20 | 0 | 0.0 | 0.0 | 16.8 | <20 | - | - | |
| | PII(M2) | 20 | 1 | 5.0 | 0.1 | 24.9 | <20 | - | - | |

GMC = geometric mean antibody concentration calculated on all subjects

N = number of subjects with available results

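### Infants with recorded rotavirus gastroenteritis stay in the anti-RV IgA results, and no planned analysis shows whether that matters

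*SAP*

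**What the plan says.** Section 5.1 of the SAP defines one ATP cohort, for immunogenicity. Its definition in 5.1.2 removes infants with concomitant infections that may have influenced the immune response, then exempts rotavirus gastroenteritis: "Note that RV GE will not be considered as concomitant infection unrelated to any component of the DPT-IPV vaccine". Section 5.2.2 repeats this in code 2070: "Concomitant infection not related to any component of the DPT-IPV vaccine other than RV GE which may influence the immune response". Code 2060 covers only infections related to DPT-IPV components, and codes 2090 and 2100 look only at Visit 7.

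Section 6.3.1 then states: "The ATP cohort for immunogenicity will be used for the primary analysis of immunogenicity". Its within-group summaries cover every antigen, and Template 10 in Annex 3 is titled "Anti-rotavirus IgA antibody GMC and seropositivity rates - ATP cohort for immunogenicity". Templates 11 (GMC in seropositive infants) and 16 (reverse cumulative curve) name the same cohort.

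The first secondary objective in Section 3.2 attributes these results to the vaccine: "To assess the immunogenicity of the liquid HRV vaccine in terms of serum anti-RV IgA antibody seropositivity". Section 5.2.4 declares visit-specific censoring not applicable. The sampling schedule in Section 2 has one sample for anti-RV IgA, a month after the second HRV dose, and none before vaccination.

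**The concern.** The infection rules are written with DPT-IPV in mind. For those antigens, keeping infants with RV GE is sensible. For anti-RV IgA the same rules work the wrong way round. An unrelated infection judged able to influence the immune response removes an infant from the IgA tables, even if it occurs after the IgA sample, because code 2070 runs to Visit 7. The infection that itself induces anti-RV IgA removes nobody.

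An infant who did not respond to the vaccine but had rotavirus infection before Visit 4 or 5 can therefore be counted as a vaccine responder. A responder who was infected may carry a boosted concentration into the GMC. Without a baseline sample, an RV GE sensitivity analysis or a listing, a reader of the report could not tell how often this happened. The fallback TVC analysis does not help, because it keeps the same infants. At stake is how the descriptive IgA results are read, not the primary objective.

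**Working it through.** **No figure to reproduce.** The SAP gives no wild-type rotavirus incidence and no sample-size or precision statement for anti-RV IgA. What follows is a range under stated assumptions.

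**Windows (Table 4, optimal intervals).**
- First HRV dose to IgA sample, Co-administration: Visit 1→2 plus 2→4 = 30 + 30 = 60 days (allowed 56 to 84).
- First HRV dose to IgA sample, Staggered: Visit 1→2, 2→3 and 3→5 = 30 + 15 + 30 = 75 days (allowed 63 to 105, or 63 to 98 with the 8-week limit on Visit 2→5).
- Second HRV dose to IgA sample: 30 days (28 to 42) in both groups.

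The Staggered window is 15 days (25%) longer, and all of the difference lies between the two HRV doses.

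**Formulas.** Infection risk P = 1 - exp(-rate × days/365.25). Rise in seropositivity = P × (1 - S), where S is the seropositivity due to the vaccine alone. Only non-responders can change status, so the rate that matters is theirs. The formula assumes that each infected non-responder is seropositive by the sample. The counts of infected infants also assume the same rate in responders.

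**Assumed inputs.** Rates of 1, 5, 10 and 30 per 100 person-years; S of 75, 85 and 95%; 73 infants per group (Section 2, Table 3). Each cell gives Co-administration / Staggered.

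| Rate per 100 person-years | Infected of 73 | Rise, S = 95% (points) | Rise, S = 85% (points) | Rise, S = 75% (points) |
|---|---|---|---|---|
| 1 | 0.12 / 0.15 | 0.008 / 0.010 | 0.025 / 0.031 | 0.041 / 0.051 |
| 5 | 0.60 / 0.75 | 0.041 / 0.051 | 0.123 / 0.153 | 0.204 / 0.255 |
| 10 | 1.19 / 1.48 | 0.081 / 0.102 | 0.244 / 0.305 | 0.407 / 0.508 |
| 30 | 3.51 / 4.36 | 0.240 / 0.299 | 0.721 / 0.896 | 1.202 / 1.494 |

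Worked example, bottom right, Staggered: P = 1 - exp(-0.30 × 75/365.25) = 0.0597, and 0.0597 × 25 = 1.49 points. The largest difference between groups is 1.494 - 1.202 = 0.29 points. At the extremes of the allowed windows (98 v 56 days) it is 0.81.

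These figures count all infections. The exception retains only those recorded as RV GE, so its own share is no larger.

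**Against precision.** The Clopper-Pearson 95% CI for 62/73 (84.9%) is 74.6 to 92.2%, about -10/+7 points. As a check, the same routine returns Template 10's printed intervals for 29/34 (68.9 to 95.0) and 1/20 (0.1 to 24.9).

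**Would censoring remove the bias?** Take a true 85.3% and infect 5% of the 14.7% who are non-responders, that is 0.735 points.
- Infants kept: 85.3 + 0.735 = 86.04%.
- Infants censored, infection only in non-responders: 85.3/(100 - 0.735) = 85.93%. Of the 0.735-point bias, 0.63 remains, about 86%.
- Infants censored, infection unrelated to response: responders and non-responders drop out in proportion, and 85.3% is recovered in full.

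Censoring therefore removes between little and all of the bias, depending on who falls ill.

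**The case against.** The strongest case against is that this is a small limitation of a descriptive endpoint. Much of that stands: the primary analysis is untouched, the plausible shift is well inside the confidence interval, and censoring on an event after vaccination is itself selective. RV GE also misses silent infection, and nothing in the SAP separates wild-type from vaccine-strain virus. The missing baseline sample is a design choice rather than an SAP error. The protocol, not shown, may exclude infants with earlier RV GE (code 2010 would then apply) and may be the source of the exception, since Section 9 lists no change to it.

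Two stronger readings are tempting, and the SAP supports neither.

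- **That the longer window biases a comparison in favour of the Staggered group.** Section 6.3.1 limits between-group assessment to the DPT-IPV antigens, and Section 7 rules out comparative analyses outside the confirmatory objectives. The window after the second HRV dose is equal.
- **That Template 10 shows a material natural infection rate.** It prints 1 of 20 placebo infants seropositive after the second dose ("PII(M2) | 20 | 1 | 5.0 | 0.1 | 24.9"). With 14.7% non-responders, 5% would add 0.147 × 5 = 0.7 points and the upper limit of 24.9% would add 3.7. With that infant's 496 U/mL from Template 11, the GMC would rise by about 3% or 15%. But Annex 3 says the mock data are illustrative and copied from other studies. The rate is one unvaccinated infant, not recorded as having RV GE, whereas every infant here receives HRV.

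None of this answers the textual point. The SAP decides who enters the IgA tables, and its rule was not adapted to that endpoint.

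**Conclusion.** The concern holds in a limited form. As written, recorded RV GE before the Visit 4/5 sample does not remove an infant from any anti-RV IgA result, and nothing planned shows how much those infants contribute. Inflation of seropositivity is probably about 0 to 1.5 points per group at the optimal intervals, with at most 0.3 points between groups. Both rest on assumed incidences and assumed vaccine seropositivity. I give no size for the GMCs, because the SAP has no concentration for infected vaccinated infants. The 75 v 60 day window is a minor detail. This is a modest improvement to a descriptive secondary endpoint. It is no threat to the non-inferiority conclusion and no reason to drop the exception for DPT-IPV.

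**What to change.** Leave 5.1.2 and code 2070 as they are for the DPT-IPV antigens. In 5.2.4, replace the not-applicable entry with a rule specific to anti-RV IgA: flag the IgA result of any infant with RV GE recorded before the Visit 4 (Co-administration) or Visit 5 (Staggered) sample. In 6.3.2, state that seropositivity, GMC, GMC in seropositive infants and the reverse cumulative curve will be shown with the flagged results included and again with them censored. List the flagged infants by group.

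The cost is a few sentences, one flag in the IgA dataset and a second set of IgA outputs, with no new procedure. A few results drop from the censored version of a sub-cohort of 73 per group. Silent infection is still not captured, and censoring may also remove true vaccine non-responders. That is why both versions should appear and neither should replace the other. If no infant is flagged, the listing says so and the question is closed.

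### The single ATP immunogenicity cohort is tied to DPT-IPV at Visit 7, so valid earlier anti-RV IgA results can be dropped for later events and may reach no analysis

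*SAP*

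**What the plan says.** SAP Section 5.1 states: "Two cohorts are defined for the purpose of the analysis". These are the TVC and one ATP cohort for immunogenicity. Section 5.1.2 admits to the ATP cohort only infants "for whom immunogenicity data are available for at least one antigen of the DPT-IPV vaccine at visit 7 sampling time point".

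The elimination codes in Section 5.2.2 follow the same anchor:

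- Code 2040 is "Administration of any medication forbidden by the protocol up to blood sample at visit 7". Codes 1040 and 2050 to 2070 have the same end point.
- Code 2090 is "Non compliance with blood sample schedule at Visit 7".
- Code 2100 applies to "serological data missing for all antigens in the DPT-IPV vaccine at Visit 7".
- Code 2080 uses Table 4, which includes the intervals from Visit 4 or 5 to Visit 6.
- Codes 1070 to 1090 concern how any study dose was given, so the third DPT-IPV dose can set them.

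Sections 5.2.3 and 5.2.4 declare right censoring and visit-specific censoring not applicable. Section 9 records that the protocol's rule referred to results at both sampling time points (Visits 4/5 and 7), and that the SAP now excludes on Visit 7 alone.

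The IgA endpoint in Section 4.2 is "Serum anti-RV IgA antibody concentration and seropositivity in a sub-cohort of subjects, 1 month after the second dose of the liquid HRV vaccine". Section 2 defines who provides it: "The sub-cohort will consist of 146 subjects (the first 73 subjects enrolled into the study from each study group").

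Section 6.3.1 makes the ATP cohort the primary set for immunogenicity without separating IgA, and Templates 10, 11 and 16 place the IgA tables and curves on it. For the TVC, Section 5.1.1 says: "An immunogenicity analysis based on the TVC will include all subjects from this cohort for whom immunogenicity data were available". Section 6.3.1 makes that analysis conditional on ATP exclusion of more than 5% of vaccinated subjects who have immunogenicity results.

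**The concern.** The cohort's criteria match the DPT-IPV endpoint but not the IgA endpoint. With no visit-specific censoring, one elimination code removes the infant from every immunogenicity table. A compliant IgA sample taken at Visit 4 or 5 is discarded because of an event that had not yet happened and cannot alter the result.

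The fallback is poorly aimed at this loss, for two reasons:

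- Its 5% trigger is counted over all infants with any result, while IgA comes from half of them.
- An infant outside the sub-cohort gives blood only at Visit 7. If that visit is missed, the infant has no result and does not enter the count. Missed Visit 7 samples therefore count only when they come from the sub-cohort, yet they are measured against the whole trial.

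Below the trigger, the dropped IgA results appear in no planned analysis. What is at stake is completeness and some precision of a secondary endpoint for which infants were specifically bled.

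**Working it through.** **Inputs.** SAP Section 2 gives 146 infants per group, 292 in total, and a sub-cohort of 73 per group. Check: 2 × 73 = 146, and 146/292 = 50%, which agrees with Table 3. The trigger, more than 5%, is from Section 6.3.1. The SAP gives no exclusion rate and no expected IgA seropositivity, so those values below are assumptions.

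**1. Where the trigger fires.** Suppose all 292 infants have at least one result.

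- 14 excluded: 14/292 = 4.8%, not fired.
- 15 excluded: 15/292 = 5.1%, fired.

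Applied to the sub-cohort alone, the same rule would fire at 8 exclusions (8/146 = 5.5%).

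**2. How many IgA results can end up in no analysis.** Three patterns of exclusion:

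| Pattern | Trigger count | Fired? | IgA results unanalysed |
|---|---|---|---|
| Equal in both halves, all counted, 7 per half | 14/292 = 4.8% | No | 7/146 = 4.8% |
| Same, 8 per half | 16/292 = 5.5% | Yes | none |
| Only missed Visit 7 after the IgA visit, 13 per half | 13/(292 − 13) = 13/279 = 4.7% | No | 13/146 = 8.9% |
| Same, 14 per half | 14/(292 − 14) = 14/278 = 5.04% | Yes | none |
| All counted exclusions in the sub-cohort, 14 | 14/292 = 4.8% | No | 14/146 = 9.6% |

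In the 13-per-half case, 26/292 = 8.9% of all infants miss Visit 7. The 13 outside the sub-cohort have no result, so they leave both the numerator and the denominator of the trigger.

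**3. How fragile the larger figures are.** The 9.6% ceiling needs no counted exclusion outside the sub-cohort. If 14 exclusions fell at random among 292 infants, the chance that all were in the sub-cohort is C(146,14)/C(292,14), about 4 in 100,000. The 8.9% case needs no exclusion under any other code: one more among the 279 infants with results gives 14/279 = 5.02%, and the TVC analysis runs.

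**4. Effect on precision.** Assume 73 IgA results per group, about 85% seropositive, and loss unrelated to IgA. The exact (Clopper-Pearson) 95% intervals are:

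- No loss: 62/73 = 84.9%, 74.6% to 92.2%.
- About 10% loss (66 left): 56/66 = 84.8%, 73.9% to 92.5%.

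To avoid rounding of counts when other rates are assumed, use the expected count np in the same formula:

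| Assumed seropositivity | n = 73 | n = 66 | Lower limit falls (points) | Upper limit rises (points) |
|---|---|---|---|---|
| 70% | 58.1 to 80.2 | 57.5 to 80.7 | 0.7 | 0.5 |
| 85% | 74.7 to 92.3 | 74.1 to 92.6 | 0.6 | 0.3 |
| 95% | 87.2 to 98.7 | 86.7 to 98.8 | 0.6 | 0.1 |

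(Changes are computed before rounding.)

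**The case against.** The strongest reply is that this is a declared choice and not an error. Sections 5.1.2, 5.2.2 and 9 agree with one another, and Section 9 states the change openly. One cohort also lets the HRV and DPT-IPV responses be described in the same compliant infants, which has some logic in a co-administration trial. The TVC analysis exists to show whether ATP exclusion has biased the results. A sub-cohort infant with IgA but no Visit 7 result does count towards its trigger, so the trigger is diluted rather than blind. The larger figures are corner cases, and in the symmetric case the unanalysed share, 4.8%, lies within the SAP's own 5% tolerance. IgA has no success criterion, and Section 7 rules out comparative analyses of such endpoints.

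Most of this stands, and it limits the weight of the point. It does not remove it. Section 9 gives no reason for dropping the Visit 4/5 time point from the rule and supplies no separate IgA set. Describing both vaccines in the same infants is a fair aim, but the IgA endpoint as written does not need it, and a separate set would not prevent it for the DPT-IPV tables. A diluted trigger still leaves a range of exclusions in which valid IgA results are analysed nowhere.

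**Conclusion.** The point holds as an optional improvement. Followed as written, the SAP discards valid anti-RV IgA results for events after the sample, and the conditional TVC analysis need not recover them.

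The most reasonable single figure is up to 7 of 146 results (4.8%), which assumes equal, fully counted exclusions in the two halves. The 8.9% and 9.6% figures are extremes that depend on the conditions shown above. These are limits on what the rule allows, not forecasts, because the SAP gives no exclusion rate.

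The practical effect is small. With loss unrelated to IgA, a 10% loss lowers the lower limit by 0.6 to 0.7 points and raises the upper limit by 0.1 to 0.5 points, for assumed seropositivity of 70% to 95%. No bias is shown, and the primary DPT-IPV non-inferiority analysis is untouched.

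**What to change.** Add to Section 5.1 an ATP set for HRV immunogenicity, made up of sub-cohort infants who:

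- have an anti-RV IgA result;
- complied with HRV dosing;
- kept the Visit 2 to 4 interval (Co-administration group) or the Visit 3 to 5 interval (Staggered group) already given in Table 4;
- have no elimination code arising up to the Visit 4/5 sample.

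Use this set for the anti-RV IgA tables and reverse cumulative curves, and keep the present cohort for the DPT-IPV antigens.

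The cost is one more analysis set, built from data already collected. The drawback is that the IgA tables will carry a different N from the DPT-IPV tables, so the two responses will not be described in exactly the same infants. A footnote can state this.
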